5.1 Methodological Considerations

SAS software (version 9.4 or higher) will be used for all data analyses and tabulations.

Two-sided hypothesis testing will be conducted for all inferential analyses. Resulting p-values less than 0.05 will be considered statistically significant. To control the overall error rate, a hierarchical approach will be applied. Upon the significance of the primary efficacy outcome, secondary endpoints will be analyzed and no adjustment to the p-values will be applied to multiple comparisons. For this non-inferiority study, the null hypothesis to be tested for all the secondary endpoints is that there is no difference between the two products, and all statistical comparisons for these endpoints will be considered descriptive (non-inferential).

No interim analyses are planned.

All the data points will be presented in subject data listings.

5.2 Handling of Dropouts or Missing Data

For demographics, baseline characteristics, safety profile and other evaluations, each variable will be analyzed using the existing data. Subjects with missing data will be excluded only from the analyses for which data are not available.

No missing values will be replaced in the PP analyses. There will not be missing data for the primary efficacy endpoint for the PP population based on the PP definition in Section 4.

Only for the overall LFGS and its derivatives for the mITT analysis, missing scores will be replaced using the multiple imputation (MI) approach for the mITT analysis only. Depending on the pattern of missingness, a two-step process may be employed. If missing data occur for an intermediate visit, they will be imputed first via a Markov Chain Monte Carlo (MCMC) method. As a result, a monotone missingness pattern will be obtained for the data to be fully imputed. The subsequent imputation will use Monotone Regression to produce 5 imputed datasets where the remaining missing data are filled in.

When missing overall LFGS score at a given visit is imputed, the values from all its previous visits will be included as predictor in the imputation model. For example, for a subject with missing overall LFGS at Visit 4, the overall LFGS scores from Visits 1 through 3 for the subjects will be included in the imputation model. Other variables that go into the imputation models include treatment, site, and key baseline characteristics of age, gender, race and Fitzpatrick skin type.

To prepare for MI, for subjects who are early discontinued from the study, their efficacy data captured at the termination visit will be assigned to the nearest corresponding scheduled visit.

The SAS code for MI is as follows, using the random number 69833 as the seed for the first Step and 192185 as the seed for the second step. Where notation of main variables:

- Trt = treatment: 1 for Test product, 2 for competitor product
- Invid = site number
- Age = subject's age

- Sexn = gender: 1 for female, 2 for male
- Nrace = race: 1 for White, 2 for Asian, 3 for Native Hawaiian or Other Pacific-Islander, 4 for Black or African American, 5 for American Indian or Alaska Native, 6 for Other, 7 for Mixed
- Fstn = Fitzpatrick skin type in numeric value
- v1 - v5: LFGS at Visits 1-5 accordingly

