### **7.6.12 Evaluation for Touch-up**

The Treating Investigator will evaluate the subject at Visit 2 and determine in consultation with the subject the need for a touch-up treatment.

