**7.7.3 Visit 2/Day 28 ( $\pm$  2 days): Interim Visit at Month 1 with Possible Touch-up Treatment**

- LFGS assessments
- POL assessments
- pGAI assessment
- iGAI assessment
- Lip function evaluation prior to treatment administration if applicable
- Lip sensation evaluation prior to treatment administration if applicable
- Lip texture evaluation prior to treatment administration if applicable
- Lip firmness evaluation prior to treatment administration if applicable
- Lip symmetry evaluation prior to treatment administration if applicable
- Lip movement/function evaluation prior to treatment administration if applicable
- Vision Evaluation (Snellen visual acuity, confrontational visual fields, ocular motility)
- Swelling Assessment
- Subject satisfaction with lips (VAS)

- Treatment administration if touch-up is needed (at Treating Investigator's discretion)
- Vision Evaluation (Snellen visual acuity, confrontational visual fields, ocular motility) 30 minutes after treatment if applicable
- Investigator Ease of Use assessment if applicable
- Assess AEs
- Assess concomitant medications/treatments
- Collect subject diary card
- Dispense new subject diary card if touch up treatment is given
- Schedule next visit
- Complete CRFs

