***Step 2: MI regression;**

```
PROC MI data=step1 out=step2 seed=192185 nimpute=5;  
  var trt invid age sexn nrace fstn v1 v2 v3 v4 v5;  
  monotone reg(v2 = trt invid age sexn nrace fstn v1); *for missing at v2;  
  monotone reg(v3 = trt invid age sexn nrace fstn v1 v2); *for missing at v3;  
  monotone reg(v4 = trt invid age sexn nrace fstn v1 v2 v3); *for missing at v4;  
  monotone reg(v5 = trt invid age sexn nrace fstn v1 v2 v3 v4); *for missing at v5;  
run;
```

The imputed values will be round to integer and within the range of 0 to 4.

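### The mITT imputation model for overall LFGS leaves out the Visit 2 touch-up, so missing Month 2 scores are predicted from a mix of re-injected and untouched subjects

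*SAP*

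**What the plan says.** SAP 5.2 imputes only overall LFGS and the measures derived from it, and only for the mITT analysis. For a missing visit, "the values from all its previous visits will be included as predictor in the imputation model". The remaining predictors are listed as follows: "Other variables that go into the imputation models include treatment, site, and key baseline characteristics of age, gender, race and Fitzpatrick skin type". The code agrees with the text. The Month 2 model in Step 2 is "monotone reg(v3 = trt invid age sexn nrace fstn v1 v2); *for missing at v3", and the Step 1 MCMC list holds the same covariates and all five visit scores. After Step 2, "The imputed values will be round to integer and within the range of 0 to 4".

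On the touch-up, Protocol 7.7.3 puts the LFGS assessment at the head of the Visit 2 list and "Treatment administration if touch-up is needed" further down. Under Protocol 7.6.12 the Treating Investigator is to "determine in consultation with the subject the need for a touch-up treatment"; no LFGS threshold is set. Touch-up exposure is recorded: SAP 5.6.2 summarises the amount used at Visit 2, and Listing 16.2.5.1 shows treatment by subject and visit.

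SAP 5.5.1 makes the PP result definitive and the mITT result supportive. PP data are not imputed.

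**The concern.** The touch-up is a second dose of the study device given between the Visit 2 score (a main predictor) and the Visit 3 score (the primary endpoint). Because it is discretionary, the Visit 2 score does not determine it. A model without it averages over re-injected and untouched subjects, and that average is wrong for each kind of dropout. Touch-up status could also be related to who leaves, and missing-at-random is then less credible when the model ignores it.

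At stake is the mITT analysis, which is the main planned check on subjects lost from the definitive PP set. The same imputed scores feed the LFGS responder endpoint and the Month 3 and Month 6 changes.

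**Working it through.** **1. What the documents fix.** They give no touch-up rate, touch-up gain or missing-score rate. The one loss figure is the 80% PP share in SAP 3.2: 126 / 0.80 = 157.5, rounded up to the stated 158. The allowance is therefore 158 − 126 = 32 subjects for all PP exclusions together. It is used here only as a rough ceiling of 20% missing. Every other rate below is an assumption.

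**2. Structure.** Suppose a touch-up adds *e* grades to the Month 2 score, given the Visit 2 score. Let *r* be the touch-up rate among comparable observed subjects. A model without the touch-up gives everyone the average gain *e·r*:

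- untouched dropout: error = +*e·r*
- touched-up dropout: error = *e·r* − *e* = −*e*(1 − *r*)

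With *e* = 0.6 and *r* = 0.5 these are +0.30 and −0.30 grade. If a share *m* of an arm is missing and a share *u* of those were untouched, the arm mean is off by *m·e*·[*u·r* − (1 − *u*)(1 − *r*)]. When dropout is unrelated to touch-up, *u* = 1 − *r* and this is zero. When all losses precede Visit 2, *u* = 1 and it is *m·e·r*.

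**3. Arm difference when losses precede Visit 2:** *e*·(*m*T·*r*T − *m*C·*r*C), where positive favours the test device.

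- *e* 0.6, *m* 0.20 in both arms, *r* 0.5 vs 0.3: 0.6 × (0.10 − 0.06) = +0.024
- *e* 0.6, *m* 0.10 in both arms, *r* 0.3 vs 0.5: 0.6 × (0.03 − 0.05) = −0.012
- *e* 1.0, *m* 0.10 vs 0.20, *r* 0.3 in both arms: 0.03 − 0.06 = −0.03
- equal *m* and *r*: 0

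Of 21 settings tried, three passed 0.03: 0.04, 0.054 and 0.09. All three need 20% of the test arm lost before Visit 2, which alone would use up the whole PP allowance.

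**4. Simulation on the mean scale.** Test device 0.3 grade weaker at Visit 2, touch-up gain 0.6. Entries are the bias in the arm difference at 10% / 20% missing; positive favours the weaker test device.

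| Who is lost | Touch-up follows Visit 2 gain only | Test arm touched up more at same score | Test arm touched up less at same score |
|---|---|---|---|
| Before Visit 2 | +0.006 / +0.008 | +0.015 / +0.030 | −0.005 / −0.009 |
| After Visit 2, untouched only | 0.000 / −0.001 | −0.005 / −0.018 | −0.001 / −0.001 |
| After Visit 2, touched-up only | −0.001 / −0.004 | +0.001 / +0.002 | +0.002 / +0.008 |
| After Visit 2, at random | 0.000 / 0.000 | −0.001 / 0.000 | +0.001 / 0.000 |

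With a touch-up indicator, every entry is within about 0.002 of zero.

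**5. Simulation on the 0–4 grades, adverse setting.** 79 per arm, five imputations. Month 1 gain has mean 1.5 (control) or 0.8 (weaker test arm), SD 0.85. Touch-up probability is 0.65 / 0.45 / 0.2 for a gain of ≤0 / 1 / ≥2. Leaving probability is 0.45 / 0.2 / 0.06 for the same groups if untouched, and 0.05 if touched up. About 12% (control) and 15% (test) are missing. At a touch-up effect of 0.8:

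| | Truth | SAP model | Touch-up + predictive mean matching |
|---|---|---|---|
| Response among imputed | 52.7% | 61.7% | 53.8% |
| Arm difference, grades | −0.464 | −0.443 | −0.458 |
| Arm difference, response points | −15.4 | −14.2 | −15.1 |

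Imputed response is thus 9.0 points too high, and the difference moves by 0.021 grade and 1.2 points. Over touch-up effects of 0.4 to 1.2, imputed response is overstated by about 4 to 12 points and mean change by about 0.06 to 0.25 grade. The difference moves by about 0.01 to 0.03 grade. With equal arms it does not move.

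**6. Effect on the planned limits.** Across reruns of this adverse setting, the Hodges-Lehmann lower limit was the same under both models in roughly 82 to 96% of trials. In one rerun at effect 0.8 (site and demographics left out), the non-inferiority decision agreed in all trials at the −1.0 limit of SAP 5.5.1. At the −0.50 limit of Protocol 8.2 it agreed in 98% (7.1% against 5.5% passing). That the two limits differ is a separate matter.

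**7. Rounding and clipping.** With purely random dropout after Visit 2, rounding and clipping understated imputed response by about 1 to 3 points. In the adverse setting it hardly mattered. In the same rerun, touch-up with the SAP's regression and rounding gave 54.0% imputed response against a truth of 54.3%. Predictive mean matching without touch-up gave 65.1%, so the indicator does the main work.

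**The case against.** A reader might infer that the omission favours a weaker test device. The documents do not support that. They say nothing about touch-up or dropout by arm, and the table in step 4 has both signs. The shift toward the test device in step 5 follows from the leaving rates assumed there. When untouched subjects leave after Visit 2 and the weaker arm is touched up more, the shift goes against that arm.

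A reader might also infer that all imputed scores from Month 2 to Month 6 are equally affected. They are not. The Visit 4 and Visit 5 models condition on the Visit 3 score, which already reflects the touch-up when it is observed.

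Other objections stand in part:

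- The PP result is definitive and not imputed, and secondary comparisons are descriptive.
- The mITT analysis is not the only check on PP losses, since SAP 5.3 also compares PP with non-PP subjects at baseline.
- Protocol 7.3.3 asks for the early-termination procedures, which include LFGS, and SAP 5.2 assigns those scores to the nearest scheduled visit. Fewer scores may need imputing than assumed here.
- That LFGS is scored before the touch-up is a strong inference from the order of the Protocol 7.7.3 list. Only the lip safety evaluations are expressly placed before treatment.
- The remedy is not wholly free. MCMC in Step 1 uses all listed variables jointly, so the indicator cannot be kept from informing an interim-missing Visit 2 score.

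These limit the size and reach of the point. None of them justifies leaving a known, recorded injection out of the model.

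**Conclusion.** The point holds as a small defect in a supportive analysis. The omission is plain in both text and code. It can bias imputed Month 2 response and mean change in either direction: up for untouched dropouts, down for touched-up ones. The arm difference is affected only when touch-up or dropout patterns differ between arms, by about 0.03 grade or less in the simulations. The closed-form check gives more only at the extreme losses noted in step 3. The gap is mainly at Visit 3 and reaches Visits 4 and 5 chiefly when Visit 3 is also missing. The rates are all assumed, and the mean-scale table ignores rounding and the Hodges-Lehmann step, so its sizes are indicative. Uncertainty about the direction is a reason to include the term, because it removed nearly all of the simulated bias in the arm difference whichever way that ran.

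**What to change.** Before database lock, amend SAP 5.2 as follows.

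- Define a 0/1 indicator for a touch-up actually injected at Visit 2, coded 0 if none was given, including when Visit 2 was missed.
- Place it with the fully observed variables ahead of v1 in both PROC MI variable lists. State that Step 1 MCMC uses all listed variables jointly.
- In Step 2, name it as a predictor in the v3, v4 and v5 models and leave the v2 model unchanged.
- Preferably use regpmm in Step 2 in place of reg with rounding and clipping, so that Step 2 draws are observed grades. This part is secondary to the indicator.

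The cost is one extra model term and a few words of text and code, with no new data and no change to trial conduct. The remaining weakness is a minor approximation for subjects with an interim-missing Visit 2, who are coded with those seen at Visit 2 and not re-injected.

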***Step 1: MCMC fills interim missingness to make monotone;**

```
PROC MI data=eff out=step1 seed=69833 nimpute=1;  
  mcmc impute=monotone;  
  var trt invid age sexn nrace fstn v1 v2 v3 v4 v5;  
run;
```

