5.5.1 Primary Efficacy Analysis

The primary efficacy endpoint is change from baseline to Visit 3/Month 2 in overall LFGS. The null hypothesis to be tested is that the Test device is inferior to the Control device. The results for PP are considered as definitive and those for mITT as supportive.

Summary statistics (mean, SD, minimum, median, maximum) and 95% confidence interval (CI) for mean will be presented for the changes scores for each treatment.

Due to the fact that the change scores would only contain 5 possible values (0, 1, 2, 3, and 4), the normal distribution assumption is hardly attainable, and therefore, the nonparametric Hodges-Lehmann (HL) estimators will be employed to test the study hypothesis. The 95% confidence limits for the median differences between the two treatment groups (PN40082 minus Restylane Silk) will be derived using PROC NPARIWAY with the option for the HL estimators. If the lower limit is on or above -1.0, the null hypothesis will be rejected to support the claim that PN40082 is non-inferior to Restylane Silk.

For the mITT analysis, the above analysis will be carried out for each copy of the MI data sets. Then PROC MIANALYZE will be performed to account for the between and within variation in the multiply imputed data sets.

To assist an assessment for the consistency of the treatment effect among sites, summary of the primary endpoint will be presented by site for the primary population (i.e., the PP subjects).

The primary endpoint will also be analyzed for the following two subsets of the PP subjects: (1) subjects that have injection on one lip only, and (2) subjects that have injections on both lips.

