5.5.2 Secondary Efficacy Analysis

The secondary efficacy endpoints include the following:

- percent of subjects with treatment success (responder on overall LFGS) at Visit 3/Month 2, where responder is defined as a subject with at least a 1-grade increase from baseline on the overall LFGS
- percent of responders on the overall POL severity scale at Visit 4/Month 3 (defined as a subject demonstrating ≥ 1 -point improvement, i.e., decrease in severity, from baseline)
- change from baseline to Visit 4/Month 3 in overall LFGS
- change from baseline to Visit 5/Month 6 in overall LFGS

The supporting importance of the secondary endpoints is ordered by [1] percent of subject with treatment success (responder on overall LFGS) at Visit 3/Month 2, [2] percent of responders on the overall POL severity scale at Visit 4/Month 3, [3] change from baseline to Visit 4/Month 3 in overall LFGS, and [4] change from baseline to Visit 5/Month 6 in overall LFGS.

These secondary variables will be summarized with descriptive statistics for each treatment arm and a 95% CI for the difference between treatments. For the proportion variables, the 95% CI for treatment difference will be calculated using the Wald's method, with subjects pooled from all study sites. For the change variables, the 95% CI for the median differences between treatments will be derived using PROC NPARIWAY with the option for the HL estimators.

For the mITT analysis, the LFGS-related secondary endpoints will be analyzed for each copy of the MI data sets. PROC MIANALYZE will then be performed to account for the between and within variation in the multiply imputed data sets.

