Site- Subject	Analyses	Study Visit	Subject	Swelling Assessment		Patient Global Aesthetic	Investigator Global Aesthetic Improvement	
			Satisfaction with Lips VAS	Grade	Performed By	Improvement (pGAI)	Score	(iGAI) Performed By
Treatment:								

Analyses: A = As-Treated (AT) Analyses, M = Modified Intent-to-Treat (MITT) Analyses, P = Per-Protocol Analyses

O:\Studies\ Prolenium\SYM 2018-02\Biometrics\Programs\Listing\xxx.sas ran on Month Day Year at hh mm on data from Month Day, Year.

Listing 16.2.6.2.1 – Derived Overall Lip Fullness Grading Scale (LFGS) for Modified Intent-to-Treat Population

Site-Subject	Fitzpatrick skin type	Lips Treated	Visit 1	Visit 2	Visit 3	Visit 4	Visit 5
Treatment: XX-XXX	II	Both	1	2	3	2	2, 3, 2, 2, 3

LFGS: 0=Very Thin Lips, 1=Thin Lips, 2=Moderately Thick Lips, 3=Thick Lips, 4=Full Lips.

Note: The 5 entries contained under a visit for a subject are the 5 imputed LFGS scores for the missing value through multiple imputations.

O:\Studies\ Prollenium\SYM 2018-02\Biometrics\Programs\Listing\xxx.sas ran on Month Day Year at hh mm on data from Month Day, Year.

Listing 16.2.6.2.2 – Derived Primary and Secondary Efficacy Responses on Overall LFGS and Overall POL for Modified Intent-to-Treat Population

Site-Subject	Study Visit	Lip Fullness Grading Scale (LFGS)			Perioral Lines at Rest Severity Scale (POL)		
		Overall LFGS Rating	Change from Baseline	Treatment Success [†]	Overall POL Rating	Change from Baseline	Responder ^{**}
Treatment:							
XX-XXX	4	2	-1	Y			
	5	2, 3, 2, 2, 3	-1, -2, -1, -1, -2	Y, Y, Y, Y, Y			

Change from Baseline for Visit x = Baseline – Visit x, where x=2, 3, 4, 5.

[†]Treatment success is defined as an achievement of at least a 1-grade increase from baseline on the overall LFGS.

^{**}Responder is defined as a subject demonstrating at least 1-point improvement, i.e., decrease in severity, from baseline POL severity.

Note: The 5 entries contained under a visit for a subject are associated the 5 imputed LFGS scores for the missing value through multiple imputations.

O:\Studies\ Prolenium\SYM 2018-02\Biometrics\Programs\Listing\cxc.sas ran on Month Day Year at hh mm on data from Month Day, Year.

Listing 16.2.6.2.3 – Derived Primary and Secondary Efficacy Responses on Overall LFGS and Overall POL for Per-Protocol Population

Site-Subject	Study Visit	Lip Fullness Grading Scale (LFGS)			Perioral Lines at Rest Severity Scale (POL)		

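### Supportive mITT analysis: an intermittent LFGS gap is imputed once and reused in all five data sets, and the combined Hodges-Lehmann row has no named standard error

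*SAP*

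**What the plan says.** SAP section 5.2 limits imputation to overall LFGS and its derivatives in the mITT population, and makes the two-step scheme conditional: "Depending on the pattern of missingness, a two-step process may be employed". Step 1, for intermediate visits, is coded "PROC MI data=eff out=step1 seed=69833 nimpute=1" with MCMC filling only as far as a monotone pattern. Step 2 reads that output: "PROC MI data=step1 out=step2 seed=192185 nimpute=5", with no BY statement. The text agrees with the code: "The subsequent imputation will use Monotone Regression to produce 5 imputed datasets where the remaining missing data are filled in". Imputed values are rounded to integers from 0 to 4.

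For the primary endpoint in mITT, SAP section 5.5.1 computes Hodges-Lehmann limits in each data set and continues: "Then PROC MIANALYZE will be performed to account for the between and within variation in the multiply imputed data sets". Section 5.5.2 says the same for the LFGS secondary endpoints: "PROC MIANALYZE will then be performed to account for the between and within variation in the multiply imputed data sets". The shells of Tables 14.2.1.2 and 14.2.2.3 (the latter also used for 14.2.2.4) attribute the Combined Analysis row to PROC MIANALYZE. The note to Listing 16.2.6.2.1 reads: "The 5 entries contained under a visit for a subject are the 5 imputed LFGS scores for the missing value through multiple imputations".

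PP is definitive and has no values replaced (SAP 5.5.1, 5.2). Secondary comparisons are descriptive (SAP 5.1).

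**The concern.** There are two independent faults.

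(a) Multiple imputation conveys uncertainty about a missing score by letting it differ between data sets. As coded, an intermittent score is drawn once and copied, so it is treated as if it had been observed. That defeats the purpose stated in sections 5.5.1 and 5.5.2, and the five entries in Listing 16.2.6.2.1 would be one number printed five times.

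(b) Pooling needs an estimate and a within-data-set variance from each data set. For the Hodges-Lehmann shift the SAP names no variance and gives no rule for a zero value. The only measure of spread that the table shows for the shift is its confidence interval, and on tied integer scores that interval often has no width.

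At stake is the credibility of the planned support for the PP result, and pre-specification: the choice of SE would otherwise be made after the data are seen.

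**Working it through.** **Sizing figure.** Inputs from SAP 3.2: SD 0.85, true difference 0, limit -0.50, 90% power; two-sided 0.05 from SAP 5.1. Per arm, n = 2 × [0.85 × (1.960 + 1.282) / 0.50]² = 60.7, so 61 (62 with the t distribution). The SAP's 63 is close and slightly conservative. 126 / 0.80 = 157.5, so 158, or 79 per arm. The checks below use 79 per arm and SD 0.85.

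**(a) Effect of the reused fill.** Rubin's total variance is T = W + (1 + 1/5)B, with W the mean within-data-set variance and B the between-data-set variance. If all gaps are intermittent, the five data sets are identical and B = 0. The ratio of the coded SE to the proper SE is then about √(1 - share of T that is between-imputation).

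For the difference in mean change, a simulation (400 trials per setting) gave between-imputation shares of 0.041, 0.0815 and 0.1615 at 5%, 10% and 20% Visit 3 gaps (about 8, 16 and 32 of 158 subjects). The ratios are √0.959 = 0.98, √0.9185 = 0.96 and √0.8385 = 0.92.

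For the planned Wald responder difference, a larger simulation was run: 1,500 trials per setting, baseline 0 or 1, mean change 1.0 or 1.5, between-visit correlation 0.5 or 0.7, gaps completely at random.

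| Assumed intermittent gaps at Visit 3 | 5% | 10% | 20% |
|---|---|---|---|
| SE too small by | 2-3% | 4-5% | 8-11% |
| Coverage, one fill reused | 94-95% | 93-95% | 91-95% |
| Coverage, five fills | 95-96% | 95-96% | 95-98% |

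**(b) Why the limits coincide.** The 95% Hodges-Lehmann limits are order statistics of the 79 × 79 = 6,241 pairwise differences. The lower rank is C = 6241/2 - 1.96 × √(6241 × 159/12) = 3120.5 - 563.6, so 2,556. The upper rank is 6241 - 2556 + 1 = 3,686. The limits therefore sit at about the 41st and 59th percentiles of the differences.

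Take rounded-normal integer changes with SD 0.85 (latent SD √(0.85² - 1/12) = 0.80) and mean 1.0. The probabilities of change 1, of 0 or 2, and of -1 or 3 are about 0.468, 0.236 each and 0.030 each. The chance that two subjects tie is 0.468² + 2 × 0.236² + 2 × 0.030² = 0.33. With equal arms, zeros fill roughly the 33rd to 67th percentiles, so both limits usually fall on 0.

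Simulated frequency of zero-width limits in a single complete data set, 79 per arm:

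| True shift | Baseline 0 or 1 only | 0-30% thick/full lips at baseline |
|---|---|---|
| 0 | 88-91% | 82-94% |
| -0.3 | 30-32% | 33-60% |
| -0.5 | 5-6% | 5-19% |

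A third score model gave 91-95% with equal arms.

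If all five data sets have zero width and the same estimate, T = 0 + 1.2 × 0 = 0 and the Combined row shows no uncertainty. With equal arms and baseline 0 or 1, this happened as follows at 5 / 10 / 20% gaps:
- all gaps intermittent, as coded: 87-89 / 86-87 / 84-85%
- all gaps intermittent, `nimpute` corrected: 82-83 / 77-79 / 68-72%
- all gaps terminal: 81-83 / 76-77 / 66-69%

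Correcting `nimpute` alone therefore does not cure (b).

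**PP.** At 63 per arm the ranks are 1,582 and 2,388 of 3,969, about the 40th and 60th percentiles. Simulated zero-width rates with equal arms were 69-86%.

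**The case against.** The other side has good points.

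- **Part (a) is small and conditional.** The two-step process is only a possibility, the effect is negligible at 5% gaps, and the responder endpoint is descriptive in a supportive population. This stands. At 20% part of the contrast also reflects a five-fill comparator that itself over-covers (95-98%).
- **The gap rate is unknown.** A reader might take 20% as an upper bound because the SAP expects 80% of randomized subjects to qualify for PP. The documents do not support that: 80% is a planning assumption and not a cap, and PP loss includes causes that leave Visit 3 observed. The rates here are illustrative.
- **The simulations omit features of the plan.** SAP 5.2 assigns termination-visit data to the nearest scheduled visit, which may reduce or move gaps. The imputation models left out site, age, sex, race and skin type. The gap-rate and Combined-row figures use baseline 0 or 1, although inclusion criterion 3 (Protocol 7.3.1) admits thick or full lips in skin types IV-VI. The direction holds, but the exact ranges should not be leaned on.
- **A mean-scale pooled row departs from the chosen method.** SAP 5.5.1 sets normality aside and SAP section 1 takes the median-difference interval from FDA comments. This stands against making a mean difference mandatory, but not against requiring that some SE be named.

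Two further inferences would go too far. The imputation is not defective for every gap: terminal gaps are drawn five times, and the worked Visit 5 example in Listing 16.2.6.2.1 is of that kind. Nor is the primary conclusion undermined by the imputation, because PP has none.

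**Conclusion.** Both faults are real and confined to the supportive mITT analysis of overall LFGS. They should be corrected before database lock, but no claim depends on them.

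Part (a) follows directly from the code and the matching text. It makes the mITT Month 2 responder interval slightly too narrow if intermittent Visit 3 gaps occur, by the amounts tabulated above under assumed rates. The Wald responder difference has its own SE, so (b) does not touch it.

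Part (b) matters more. The Combined rows of Tables 14.2.1.2, 14.2.2.3 and 14.2.2.4 have no defined method. Under the SAP's own planning assumption of equal arms, a width-based SE would be 0 in most trials: roughly 80-95% of single data sets at 79 per arm, depending on the assumed mean change and share of thick or full lips. The problem fades as the true difference approaches -0.5.

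A reader might infer that the PP analysis is wholly untouched. That is true of the imputation and the pooling only. Zero width comes from tied scores, so PP limits can coincide too.

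**What to change.** 1. Run Step 1 with `nimpute=5` or more, and Step 2 with `nimpute=1` and `BY _Imputation_`.
2. Add one SAP sentence naming the estimate and a valid, non-zero SE to be pooled in the Combined rows of Tables 14.2.1.2, 14.2.2.3 and 14.2.2.4.

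One option for item 2 is the difference in mean change with SE = √(SD₁²/n₁ + SD₂²/n₂), labelled as mean-scale. Its ingredients are already planned: "Summary statistics (mean, SD, minimum, median, maximum) and 95% confidence interval (CI) for mean will be presented for the changes scores for each treatment". With no missing data, SE = 0.85 × √(2/79) = 0.135 and the half-width is 1.96 × 0.135 = 0.265. With five fills the half-width is about 0.27 / 0.28 / 0.29-0.30 at 5 / 10 / 20% gaps, with coverage of 94-96%. Keep the per-data-set Hodges-Lehmann limits beside it, so that mITT can still be compared with PP like for like.

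The cost is a few lines of SAS, one sentence and a relabelled row, with no change to PP. The mITT responder interval becomes about 2-3 / 5-6 / 10-14% wider at 5 / 10 / 20% intermittent gaps. At mean change 1.0 its half-width goes from 13.8 to about 14.2 / 14.6 / 15.3 points. A mean-scale Combined row is not on the PP Hodges-Lehmann scale.

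The conflict between the -0.50 limit (Protocol 8.2, SAP 3.2) and -1.0 (SAP 5.5.1) must be reconciled separately; nothing here chooses between them.
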